5. CHANGES OF ANALYSIS FROM PROTOCOL

Section 3.1 of the CSP states that patients return to clinical study site at “6-, 10-, and 12-week intervals but in accordance to the study plan, patients return at 6- and 12-week intervals, with a follow-up visit at Week 62. Section 1.2 of the SAP reflects this.

Per CSP Section 12.1, a Per-Protocol (PP) analysis set is defined. However, given the limitations of PP analyses in that they lead to lack of preservation of the randomization and given the CSP states that efficacy analyses will be carried out on the Evaluable Population “and/or” the Per-Protocol population, i.e. allowing some flexibility, the team agrees to not define a PP analysis set. Additionally, an All Patients analysis set, Randomized analysis set and PK analysis set.

CSP Section 12.1 states that safety will be assessed using the ITT population, however, the team decided a safety analysis set should be defined instead. Patients would be analyzed in accordance to actual treatment received.

CSP Section 12.1 states the Evaluable population will consist of all ITT patients who receive at least 1 dose of study medication and have at least 1 post-baseline HbA1c assessment. It was decided that this definition should be modified to include at least 1 baseline and post-baseline HbA1c assessment.

CSP Section 12.2 has change in C-peptide from baseline to each study week as a secondary endpoint but this was only collected at screening and then for patients in the mixed meal sub-study at Week 52 and Week 62. Therefore this endpoint has been omitted from the SAP.

CSP section 12.2 lists the proportion of patients achieving HbA1c goals of $\leq 6.5\%$ and $< 7.0\%$ as a secondary endpoint. To align with other exenatide studies the addition of goal $< 6.5\%$ has been added.

CSP Section 12.3 states that demographic and baseline characteristics will be summarized for the ITT and Evaluable analysis sets, however the study team requested these be summarized for the ITT and Safety analysis sets.

CSP Section 12.4 states that treatment compliance will be summarized for the ITT analysis set, however, this will be summarized for the Safety analysis set.

A hierarchical testing strategy was not defined in the CSP but has been included in the SAP to protect the family-wise error rate for the primary and secondary endpoints.

CSP Section 12.6.1 states that last observation carried forward will be used for missing data at endpoint for proportion of patients meeting HbA1c goals of $\leq 6.5\%$ and $< 7.0\%$, however, patients with missing HbA1c at endpoint will be considered as non-responders. Additionally, the logistic regression sensitivity analysis described in the CSP has been replaced with a more appropriate CMH analysis using MI pattern mixture model imputation (Sections 4.2.3.4 and 4.2.3.5), as this tests the robustness of the results from the main analysis by altering the missing data assumption.

CSP Section 12.6.1 stipulates ‘The analyses of all other efficacy endpoints will be performed in ITT population.’ Upon review of the endpoints it was agreed that all endpoints related to HbA1c should be evaluated using the Evaluable analysis set.

CSP Section 12.6.1 outlines a MMRM method will be implemented for the secondary efficacy endpoint, lipids. It was agreed after blinded data review that the data could be sufficiently reviewed as summary statistics.

CSP Section 12.6.2 specifies that both baseline HbA1c and HbA1c strata will be included in the MMRM model for the primary analysis. However, these variables will be highly correlated resulting in multicollinearity in the statistical model. Therefore, HbA1c strata will not be included in the primary model. For secondary and exploratory MMRM analyses, screening HbA1c strata will be used in the model instead of continuous baseline HbA1c.

The sensitivity and supportive analyses in Section 4.2.3.4 were not specified in the CSP and have been added to further support the primary analysis and to examine the influence of missing data due to drop-out and/or receiving rescue therapy.

Section 12.6.3 of the CSP states that the proportion of patients discontinuing the study will be analyzed using a CMH test and logistic regression by visit. However, the team agreed it would be sufficient to summarize withdrawals during the study, which is presented in the disposition summary table. Hence no statistical analyses were planned for this endpoint. In the same section of the CSP, it is stated that the proportion of patients rescued due to failure to maintain glycemic control will be analyzed using a CMH test and logistic regression by visit. However, based on the observed number of patients rescued at Week 24 being low, the team agreed summaries of this endpoint would suffice. By way of a clarification to the CSP, the team also agreed that “number of rescue episodes” should be interpreted as “number of patients rescued”, given a patient is considered rescued after initiation of rescue therapy. Therefore, a summary of the cumulative proportion of patients rescued by visit will be considered sufficient to address this endpoint.

Section 12.6.3 of the CSP states that for MMRM analyses, country will be included as a covariate. However, to align to the approach for the primary endpoint, region will be used instead.

The CSP does not specify BMI percentile as an endpoint, however the study team requested this be included and therefore summaries of observed and change from baseline in BMI percentile will be provided as specified in Section 4.2.3.6 of this SAP.

The CSP does not specify eGFR as an endpoint, nor is it provided by the laboratory. However, the team felt it would provide important information for this study so it will be derived and analyzed as stated in Section 4.2.4.4 of this SAP.

Hypoglycemia analyses are not defined in the CSP. However, the team requested events be classified and summaries be included as defined in Section 4.2.4.7 of this SAP.

Free testosterone in the CSP has been outlined as calculated at Visit 5 (Week 12), Visit 7 (Week 24), Visit 9 (Week 40) and Visit 10 (Week 52). Since this endpoint is calculated using Albumin, total testosterone and SHBG and these parameters are not collected at Week 40, this visit will not be presented in the outputs.

Appendix F of the CSP (Mixed Meal Substudy) lists statistical analyses and summaries will be presented. However, due to an insufficient amount of data being collected for the study, the study team decided no formal analysis will be presented, only summary tables and listings.

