2.2 Secondary objectives

The secondary objectives of this study are:

- To compare the effects of EQW following 24 weeks of treatment to those achieved by placebo in children and adolescents with type 2 diabetes mellitus on the following:
 - Fasting plasma glucose concentration
 - Proportion of patients achieving HbA1c goals
 - Body weight and Tanner pubertal stage
 - Blood pressure and lipids
- To assess the effects of long-term exenatide once weekly therapy (~1 year) in children and adolescents with type 2 diabetes mellitus on the following:
 - Long-term safety and tolerability
 - Parameters related to glycemic control, including HbA1c, fasting plasma glucose concentration, and proportion of patients achieving HbA1c goals

- Body weight and Tanner pubertal stage
- Blood pressure and lipids
- To examine the effect of exenatide once weekly on beta-cell function (HOMA-B) and insulin sensitivity (HOMA-S) as measured by the homeostatic model assessment (HOMA) in children and adolescents with type 2 diabetes who are not taking insulin
- To assess the pharmacokinetics of exenatide once weekly in children and adolescents with type 2 diabetes

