The MMRM approach will be used to analyze the change in HbA1c, body weight, blood pressure, fasting plasma glucose, fasting insulin, lipids, HOMA-B, and HOMA-S from baseline Visit 2 (Week 0) to Visit 10 (Week 52), and each intermediate visit. The MMRM method for change in HbA1c will be the same as stated in Section 12.6.2. The models for changes in body weight, blood pressure, fasting plasma glucose, fasting insulin, lipids, HOMA-B, and HOMA S will include treatment group, visit, interaction between visit and treatment, HbA1c baseline strata ($<9.0\%$ or $\geq 9.0\%$), and country as the fixed effects, baseline of the dependent variable as the covariate, and patients as the random effects. The ML method will be used for parameter estimation. The least squares mean, 2-sided 95% confidence interval, and p-value of the difference in the endpoints of interests between the EQW and PBO groups will be provided.

Similar to the primary endpoint analysis, all observed data will be included in the MMRM and logistic regression analysis. Data collected from an Early Termination visit will be mapped to

the next closest scheduled visit. For patients who initiate rescue therapy and continue study participation, only data through the initiation of rescue therapy will be included in the MMRM and logistic regression analysis.

Because the introduction of the dual chamber pen injection device does not affect the randomization scheme or blinding of patients, no sensitivity analysis will be performed to assess the treatment effect due to change in the device.

The proportions of patients (N [%]) reporting different injection site reactions will be summarized at Visit 3 (Week 4) through Visit 10 (Week 52) using descriptive statistics.

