1.1.2 Secondary objective

The secondary objectives are:

- To compare the effects of EQW following 24 weeks of treatment to those achieved by PBO in children and adolescents with type 2 diabetes mellitus on the following:
 - Fasting plasma glucose concentration
 - Proportion of patients achieving HbA1c goals
 - Body weight and Tanner pubertal stage
 - Blood pressure and lipids
- To assess the effects of long-term EQW therapy (~1 year) in children and adolescents with type 2 diabetes mellitus on the following:
 - Long-term safety and tolerability
 - Parameters related to glycemic control, including HbA1c, fasting plasma glucose concentration, and proportion of patients achieving HbA1c goals
 - Body weight and Tanner pubertal stage
 - Blood pressure and lipids (total cholesterol, HDL, LDL, triglycerides)
- To examine the effect of EQW on beta-cell function (HOMA-B) and insulin sensitivity (HOMA-S) as measured by the homeostasis model assessment (HOMA) in children and adolescents with type 2 diabetes who are not taking insulin.
- To assess the pharmacokinetics (PK) of EQW in children and adolescents with type 2 diabetes.

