Secondary 2	Evaluable	Proportions of patients having HbA1c goals of <6.5%, ≤6.5% and <7.0% at Week 24 and at each intermediate visit	assumption of MMRM analysis. Rescue and IP discontinuation: Data after event excluded. Composite approach used, with patients with missing data at endpoint treated as non-responders. Withdrawal from study prior to Week 24: Composite approach used, with patients with missing data at endpoint treated as non-responders.	Difference in proportion of responders at Week 24 and each intermediate visit between EQW and PBO
Sensitivity to secondary 2	Evaluable	Proportions of patients having HbA1c goals of <6.5%, ≤6.5% and <7.0% at Week 24 and at each intermediate visit	Rescue and IP discontinuation: Data after event excluded. Hypothetical approach using MI pattern mixture model imputation. Withdrawal from study prior to Week 24: Hypothetical approach using MI pattern mixture model imputation.	Difference in proportion of responders at Week 24 and each intermediate visit between EQW and PBO
Other continuous secondary endpoints	ITT	Change in X from baseline to Week 24 and each intermediate visit	Rescue and IP discontinuation: Data after event excluded. Hypothetical approach due to MAR	Least squares mean difference in CFBL at Week 24 and each intermediate visit, as applicable.

				assumption of MMRM analysis. Withdrawal from study prior to Week 24: Hypothetical approach due to MAR assumption of MMRM analysis.	
Exploratory	Safety	Change in eGFR from baseline to Week 24 and each intermediate visit by baseline eGFR category	Rescue and IP discontinuation: Data after event excluded. Hypothetical approach due to MAR assumption of MMRM analysis. Withdrawal from study prior to Week 24: Hypothetical approach due to MAR assumption of MMRM analysis.	Least squares mean difference in CFBL at Week 24 and each intermediate visit.	
Sensitivity to exploratory	Safety	Change in eGFR from baseline to Week 24 and each intermediate visit by baseline eGFR category	Rescue: Data after event included. Treatment policy approach. IP discontinuation: Data after event excluded. Hypothetical approach due to MAR assumption of MMRM analysis.	Least squares mean difference in CFBL at Week 24 and each intermediate visit.	

				Withdrawal from study prior to Week 24: Hypothetical approach due to MAR assumption of MMRM analysis.	
--	--	--	--	-------------------------------------------------------------------------------------------------------	--

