4.2.3.5 Analysis of secondary variables

Summary statistics and frequency tables will be provided for all secondary endpoints by visit and treatment for the ITT analysis set during the controlled assessment period and separately for the subset of ITT patients who received open-label EQW during the extension period for the Treatment period (see Section 3.6.5 for Treatment period definition), unless otherwise stated.

Similar to the primary analysis, data including the Early Termination visit where applicable will be included in the MMRM and CMH analysis for secondary analysis variables. Data collected from an Early Termination visit will be mapped to the next closest scheduled visit. For patients who initiate rescue medication and continue study participation, data collected after the initiation of rescue medication will be excluded from analyses. Data collected after discontinuation of IP will be excluded from analyses for all secondary efficacy endpoints.

Change in HbA1c from baseline Visit 2 (Week 0) to Visit 10 (Week 52), and to each intermediate visit as applicable

The MMRM method for change in HbA1c will be used until Week 24 and to each intermediate visit, using the Evaluable analysis set, which is the same approach as stated in Section 4.2.3.3.

The least squares mean (LSM) change from baseline and SE bar by visit will be presented in a figure by treatment group. The p-value for the difference between treatment groups by visit will also be provided in the figure.

The observed values and change from baseline will be summarized by visit using descriptive statistics (mean, median, standard deviation, minimum, maximum). This will be provided separately for both the Evaluable analysis set during the controlled assessment period and for the subset of Evaluable patients who received open-label EQW during the extension period analysis set for the Treatment period.

HbA1c measures will be listed.

Change in fasting plasma glucose concentration, body weight, fasting insulin, lipids, blood pressure from baseline Visit 2 (Week 0) to Visit 7 (Week 24), Visit 10 (Week 52), and to each intermediate visit as applicable

The same MMRM approach will be used to analyze the change in body weight, blood pressure, fasting plasma glucose, and fasting insulin from baseline (Week 0) to Week 24, and each intermediate visit.

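### Lipids lose the protocol's modelled comparison with placebo and get arm-wise summaries only, although the lipid objective, the estimand row and the p-value rule in the SAP still call for a comparison

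*SAP*

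**What the plan says.** **Objective.** Protocol 2.2 sets out "To compare the effects of EQW following 24 weeks of treatment to those achieved by placebo in children and adolescents", and SAP 1.1.2 repeats it: "To compare the effects of EQW following 24 weeks of treatment to those achieved by PBO". The list beneath it includes "Blood pressure and lipids". Change in lipids is a secondary endpoint in Protocol 12.2.2 and SAP 3.2.

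**Protocol analysis.** Section 12.6.3 states: "The MMRM approach will be used to analyze the change in HbA1c, body weight, blood pressure, fasting plasma glucose, fasting insulin, lipids". For these models it promises a least squares mean, a 95% confidence interval and a "p-value of the difference in the endpoints of interests between the EQW and PBO groups will be provided".

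**SAP analysis.** Section 5 records the change for lipids: "It was agreed after blinded data review that the data could be sufficiently reviewed as summary statistics". Section 4.2.3.5 follows it. Lipids stand in the subsection title, the descriptive summaries and the listings, but the modelling sentence reads "The same MMRM approach will be used to analyze the change in body weight, blood pressure, fasting plasma glucose, and fasting insulin from baseline", and the model specification names the same four variables. No other between-group estimate for lipids appears.

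**SAP text that still covers lipids.** Table 2 (4.2.3.1) has a row for "Other continuous secondary endpoints" whose summary measure is a least squares mean difference. Section 4.2.3.2 says that p-values will be shown, as exploratory, for all secondary endpoints outside the hierarchy. Section 4.1.5 makes the MMRM the usual method for continuous variables measured repeatedly after baseline.

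**The concern.** The objective asks for a comparison with placebo, and the planned output gives each arm separately. The loss is specific: a reported treatment difference, its interval, adjustment for the patient's own baseline lipid value, and model-based handling of missing and excluded data.

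The last item bears on the estimand. SAP 4.2.3.5 drops data after rescue or after stopping study medication for the secondary efficacy endpoints, and Table 2 handles those events through the missing-at-random assumption of the MMRM. Without the model, a Week 24 arm mean averages whoever still has usable data, which is not the quantity that Table 2 defines.

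The SAP also gives an analyst conflicting instructions. Section 4.2.3.5 and Section 5 say descriptive only. Table 2 and Section 4.2.3.2 still lead the reader to expect a difference and a p-value.

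**Working it through.** **1. Side-by-side reading.**

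| Item | Protocol | SAP |
|---|---|---|
| Lipids in the 24-week comparison objective | Yes (2.2) | Yes (1.1.2) |
| Lipids a secondary endpoint | Yes (12.2.2) | Yes (3.2) |
| Lipid MMRM | Yes (12.6.3) | No (4.2.3.5, 5) |
| Difference with CI for lipids | Yes (12.6.3) | None specified |
| Estimand: LS mean difference | No estimand table | Yes, via Table 2 |
| p-value for non-hierarchy secondary endpoints | Yes for lipids (12.6.3) | Yes in general (4.2.3.2) |

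**2. Could the model be fitted?** SAP Table 3.3 gives lipids two post-baseline visits in the controlled period, Weeks 12 and 24. That meets the condition in SAP 4.1.5, so the visit schedule is no obstacle.

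**3. The planned analysis size.** SAP 1.2 gives at least 50 evaluable EQW and 20 evaluable placebo patients. SAP 1.3 gives a difference of 0.7, SD 1.0, two-sided alpha 0.05 and 74% power for HbA1c.

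- Standard error in SD units: sqrt(1/50 + 1/20) = sqrt(0.07) = 0.2646.
- Noncentrality: 0.7 / 0.2646 = 2.646, with 50 + 20 − 2 = 68 degrees of freedom.
- Power by the noncentral t distribution: 74.2%, which reproduces the stated 74%.

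This figure concerns HbA1c only. The documents give no power or SD for lipids. It serves here to confirm 50 versus 20 as the working sample size.

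**4. What the summaries allow.** SAP 4.1.1 and 4.2.3.5 provide n, mean and SD of change by visit and arm. From these a reader can form an unadjusted 95% interval for the difference in mean change, with half-width

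t(0.975, 68) × sqrt(1/50 + 1/20) = 1.9955 × 0.2646 = 0.528 SD.

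So a crude interval of about ±0.53 SD of the change can be derived by hand. It is not adjusted for baseline, region or HbA1c stratum, and it uses only patients with a usable value at that visit. How much baseline adjustment would narrow it depends on the baseline-to-Week-24 correlation, which the documents do not give.

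**5. How neighbouring variables are treated.** Blood pressure, in the same line of the objective, keeps its MMRM (4.2.3.5). BMI, weight percentile and height percentile, all exploratory, keep theirs (4.2.3.6). Estimated GFR, which SAP Section 5 says is not a protocol endpoint, is given one (4.2.4.4).

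**The case against.** The case for leaving the plan alone has real weight.

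- **The change is open and described as blinded.** SAP Section 5 exists to record such departures. A reader might infer that the model was dropped because of what the lipid results showed. Nothing in the documents supports that.
- **Descriptive output is not useless.** A reader might infer that the objective cannot be answered at all, or that arm-wise tables hide the uncertainty. Neither holds. The tables carry n and SD, so a crude interval can be derived. Tanner stage, in the same comparison objective, is only summarized in both the protocol (12.6.7.4) and the SAP (4.2.4), so comparing does not always mean modelling here.
- **Baseline imbalance is not shown.** A reader might infer that 5:2 allocation makes imbalance likely. Allocation is randomized; the ratio costs precision but does not bias the difference. Chance imbalance is possible, as in any small trial, and lipids are not a stratification factor.
- **Nothing confirmatory depends on it.** Lipids are outside the four-endpoint hierarchy in SAP 4.2.3.2.
- **Some of the SAP wording is elastic.** Section 4.1.5 states a general rule, and the Table 2 summary measure carries a qualifier on applicability. Section 5 can be read as the exception to both.

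These points limit the consequence. They do not supply the missing estimate, and the p-value sentence in 4.2.3.2 carries no such qualifier. The stated reason is also thin. Several other reductions in Section 5 rest on the data: C-peptide was not collected at the needed visits, few patients were rescued, and the meal substudy yielded too little. For lipids, as for study discontinuation, the SAP says only that summaries suffice.

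**Conclusion.** The point holds as a gap in reporting and consistency on a secondary objective. The SAP removes the protocol's modelled lipid comparison and plans no baseline-adjusted, missing-at-random-based treatment difference with a confidence interval. Its own objective, estimand row and p-value rule still lead the reader to expect a between-group result.

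The consequence is limited. A crude interval of about ±0.53 SD remains derivable, assuming 50 and 20 patients with usable Week 24 lipids and a common SD; with fewer patients it is wider. The primary result and the family-wise error rate are untouched. The documents do not support the stronger inferences of selective reporting, of an unanswerable objective, or of probable baseline imbalance. The change is worth making because it restores what was pre-specified at very little cost.

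**What to change.** Add total cholesterol, HDL, LDL and triglycerides to the secondary-endpoint MMRM in SAP 4.2.3.5, using the terms already written there: treatment, visit, their interaction, region, baseline of the variable, its interaction with visit, and screening HbA1c stratum. Report the EQW minus placebo LS mean difference with 95% CI at Week 24, with Week 12 as the intermediate visit. Label the results exploratory and outside the hierarchy, and amend the lipid entry in Section 5. Log-transforming triglycerides is optional; neither document asks for it.

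If the sponsor prefers to stay descriptive, the minimum is to say so against the lipid part of the objective, give the reason, and add the exception to SAP 4.1.5, Table 2 and 4.2.3.2.

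The cost is existing model code run on four more variables. The downside is a few more nominal estimates without multiplicity control, which the exploratory label covers.
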